11.3. Sample Size Determination

The target sample size for Phase I (around 10,000 households enrolled over one month, and around 21,000 individuals) was determined based on a conservative assumption that all members of the same household have the same infection status, and therefore each household should only be counted as one unit in the sample size calculation. If infection status varies within households, this will increase precision around our estimates.

The precision (margin of error) that various sample sizes provide around various estimates of infection rates (and seroprevalence) is illustrated in **Figure 5** below, together with the precision for smaller sample sizes, which should be achieved for specific regions and/or groups defined by other characteristics such as age. For a given prevalence p and sample size N, the expected margin of error corresponds to the expected width of the 95% confidence interval associated with the point estimate of p obtained using an exact binomial test. On balance, around 10,000 households in Phase I (around 21,000 individuals), and around 12,000 households (25,000 individuals) each subsequent month (3,000 per week) in Phase II, was

Clinical Research Protocol Template version 15.0

© Copyright: The University of Oxford and Oxford University Hospitals NHS Foundation Trust 2019 Page 67 of 113 considered to provide sufficient precision across England overall, particularly at lower prevalence rates which may be expected at earlier cross-sectional surveys, as well as the possibility of assessing evidence for variation within smaller but very important subgroups, including regions and Devolved Administrations (each targeting ~1,000 households per month, ~2,100 individuals per month).

However, a major concern was the ability to monitor regions, rather than England as a whole, by October 2020 when the winter season of respiratory infections started, and monitoring for a possible "second wave" of infections was critical. Therefore scaling up of recruitment from the end of July 2020 was designed to achieve similar numbers regionally as were originally available in England as a whole in Phase I, i.e. ~15,000-20,000 individuals with swab test results at least once each fortnight in each of the nine government office regions of England and also proportionate samples in Wales, Scotland, and Northern Ireland. Overall the swab target is therefore ~150,000 individuals with swab test results at least every fortnight in October in England, ~9,000 in Wales, ~5,000 in Northern Ireland and ~15,000 in Scotland (total 179,000 across the UK) (absolute numbers reflecting the relative size of the underlying populations). Sampling may be increased in regions or occupations with any evidence of increasing prevalence, in order to provide greater certainty regarding the probability of increasing infection rates as opposed to sampling variation.

For blood sampling for seroprevalence, initially 10-20% of those enrolled providing blood samples from recruitment was considered to provide an acceptable trade-off in terms of precision, given that seroprevalence rates are expected to be higher than infection rates, and so margins of error for the former can be larger than the latter without compromising decision-making. However, in order to assess the impact of vaccination, larger numbers are needed. The total blood target of ~125,500 adults 16 years and older sampled every month in England for approximately one year from March 2021 through to April 2022 (allowing time for scale-up in additional recruitment to blood sampling) was designed to provide estimates of immunity within different regions (~10,000-15,000 per month) with a margin of error below 2%, and within different age groups over 16 years within regions (~2,000 per month) with margins of error below 5% (5(c)). For those aged 8-15 years, the target was to achieve ~3,600 blood test results every month. This will achieve a margin of error below 3.3% across the UK, regardless of the underlying true seropositivity rate, compared with below 2.7% for the original target of ~5,500 blood test results per month estimated in protocol v12.0. This modest drop is still considered to provide acceptable precision. Further, for example, 3,600 test results per month would provide 85% power to detect differences in seropositivity of 50% vs 55% between those aged 8-11 vs 12-15 (assuming these age groups are approximately equally sized), so this sample size retains excellent power to look at smaller age categories within the 8-15 year olds. Further, there are currently no representative large scale surveys of antibody positivity across the UK in this age range, where questions exist about the value of extending vaccination to younger ages, uptake of vaccination, two vs one doses etc. 3,600 blood test results per month would therefore provide a substantial increase in the information available on which to base decisions, over the current status quo.

[figure not shown]
However, following maintenance of COVID-19 hospitalisation rates below levels that would overwhelm the NHS during the Omicron wave in December 2021-January 2022, and given ongoing infection rates above 3%, the need to maintain this level of precision around estimates of swab positivity has reduced. Therefore, as part of adapting to live with COVID-19, from April 2022 onwards, the swab targets will be reduced by ~25% and the blood targets by ~20% (i.e. retaining a greater percentage of those giving blood

in order to maintain as much precision as possible to monitor declines in antibodies, particularly in older age groups), to achieve the following:

- Swab target: up to ~227,300 swab samples taken from individuals 2 years and older every 28 days in England, ~15,650 in Wales, ~10,050 in Northern Ireland and ~23,200 in Scotland (~276,200 total across the UK every 28 days, ~300,000 swab samples in total across the UK per month)
- Blood target: up to ~90,850 blood samples taken from individuals 8 years and older every 28 days in England, ~6,300 in Wales, ~4,150 in Northern Ireland and ~9,200 in Scotland (~110,500 in total across the UK every 28 days, ~120,000 blood samples in total across the UK per month)

Reductions are proportionately less in Wales and Northern Ireland in order to maintain power within these countries, and proportionately more in England to meet the overall reductions. These numbers are considered to provide sufficient precision to monitoring infection rates and seroprevalence moving forwards, overall and by region/country, particularly given current levels of infection and antibody positivity. Targets are based on samples taken and arriving at the laboratories for testing rather than valid results received from the laboratories because assay failures also contribute to testing costs. Test failures with samples taken at study worker visits have generally been ~1% for swab tests and ~1.5% for blood tests; even if these increase with postal/courier return to 1-2% or 3-4% respectively, the sample targets above will retain reasonable precision. Test failure rates will be monitored closely, as will rates of samples that have been reported to have been taken failing to arrive at the consolidation hub (the latter are not included in the targets above).

[figure not shown]
Figure 5 Impact of sample size on precision for various estimates of prevalence

(a) With prevalence ranging from 0 to 10% on an absolute scale

Clinical Research Protocol Template version 15.0

[figure not shown]
© Copyright: The University of Oxford and Oxford University Hospitals NHS Foundation Trust 2019 Page 69 of 113

(b) With prevalence ranging from 0 to 10% on a log scale to highlight the impact at low prevalences

Note: straight lines indicate where the denominator does not allow more accurate estimation: eg out of 100 individuals, all true prevalences of under 0.5% correspond to 0/100 individuals.

(c) With prevalence ranging from 5 to 95% on an absolute scale

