9.9.3 Pilot community respiratory surveillance

Given the lack of circulating other respiratory viruses, influenza in particular, since the start of the COVID-19 pandemic in 2020, there is considerable concern about the potential for substantial morbidity due to influenza and other respiratory viruses in the Autumn and Winter of 2022/23. Current influenza surveillance is predominantly syndromic, testing symptomatic adults presenting to specific general practices in the Royal College of General Practitioners network every week. There is no representative community surveillance including asymptomatic individuals (estimated to comprise approximately 14% of cases in the Fluwatch study) or children.

From September 2022, in order to provide initial information on community circulation of respiratory pathogens, a pilot community respiratory surveillance study will be nested within the CIS. Every week, around 750 residual pathogen RNA extracts from randomly selected nose and throat swabs will be sent, after testing for SARS-CoV-2 testing, for additional testing for influenza and potentially RSV. A random selection of assay plates will be made at the laboratory on one day of each week and shipped for testing. This is feasible and should provide an approximately random selection of survey participants, including symptomatic and asymptomatic and across age groups and regions. Samples are only identified at the laboratory by barcodes so it is not possible to stratify sample selection by any participant characteristics such as age or region. Depending on capacity, tests will either be done at the Rosalind Franklin Laboratory using the TaqPath™ COVID-19, FluA/B, RSV Combo Kit or at the UKHSA laboratories at Colindale using an influenza multiplex assay identifying sub-types A/H1/N3/B, basarrive ed on primers/probes designed in house. As only a very small number of the ~69,500 swab samples taken each week will be tested within this pilot (~750, ~1%), and these will be from a completely random set of participants, different each week, and because the expectation is to find very few positive results (see below), results of these additional tests will not be returned to participants. Results of standard SARS-CoV-2 testing will be returned as normal.

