The primary goal of this pilot study is to identify a tipping point of community influenza prevalence such that in ~2-3 weeks time, hospitals will start to see substantial numbers of cases. Testing 750 samples and observing zero influenza cases provides an estimate of community prevalence of 0% with a 95%

confidence interval up to 0.5%, allowing us to rule out virus circulating in more than 0.5% of the community. Testing a smaller number of 400 samples per week for RSV (laboratory dependent) would provide an upper 95% confidence interval of 1%, allowing us to rule out virus circulating in more than 1% of the community. If positives are observed, estimates may be provided by age and other characteristics depending on numbers. Extracted viral RNA will be sequenced for all positives, in order to provide early information on circulating variants in order to assess congruence with the winter season's flu vaccine components.

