11.2. Description of the Statistical Methods

For the primary outcome, Bayesian dynamic spatiotemporal multi-level regression with poststratification (MRP) will be used to investigate changes in positivity rates over calendar time.^{25,26} Potential spatial correlation between neighbouring areas is taken into account using a "BYM2" specification. Time will be allowed to vary in a non-linear fashion by using a first-order autoregressive term for time. Space-time, and space-age interactions will be included to allow the positivity over time to vary by age and age group. This spatiotemporal MRP is an extension of the spatial MRP method developed by Gao et al.²⁷ In extensive simulations, Gao et al found that bias was significantly reduced when using a BYM2 specification compared to a non-spatial independent identically distributed specification. Attenuation in absolute bias was most apparent with small sample sizes. Even when simulating outcome data as a multivariate independent normal, BYM2 spatial prior produced nearly same posterior estimates as independent identically distributed prior, indicating that the BYM2 spatial prior does not force spatial structure when it is not present.

The reason for using MRP as the primary method is because it allows probabilistic assessment of relatively rapid changes in positivity. MRP consists of two steps. First, a multilevel regression model is used to generate the outcome of interest as a function of (socio)demographic and geographic variables. Next, the resulting outcome estimates for each demographic-geographic respondent type are poststratified by the percentage of each type in the actual overall population. In several empirical and simulation studies MRP was superior at both the national and regional levels to classical survey weighted and unweighted approaches, including when using small sample sizes.^{26,28} Factors included in the main models - besides time, space, and a space-time interaction described above – will be sex, age, ethnicity and an age-time interaction. Whether additional interactions are needed will be determined based on the Watanabe-Akaike information criterion.

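### The blood-sampling margins of error in 11.3 count individuals as independent although blood is sampled by household, and two of them have almost no slack near 50% seropositivity

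*Protocol*

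**What the plan says.** Section 11.3 starts from a cautious position. Phase I was sized as if "all members of the same household have the same infection status, and therefore each household should only be counted as one unit". It then fixes the measure of precision: "the expected margin of error corresponds to the expected width of the 95% confidence interval associated with the point estimate of p obtained using an" (the method named next is the exact binomial test). Margin of error therefore means the full width of the interval, not half of it.

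The blood targets that follow are numbers of people:

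- Adults by region, about 10,000-15,000 a month, "with a margin of error below 2%, and within different age groups over 16 years within regions" (about 2,000 a month) below 5%.
- Ages 8-15, about 3,600 results a month: "This will achieve a margin of error below 3.3% across the UK, regardless of the underlying true seropositivity rate". The earlier target of 5,500 is said to have given below 2.7%.
- 3,600 results are said to give 85% power for 50% against 55% between ages 8-11 and 12-15.

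Section 7 says that blood is drawn from all willing participants in a selected household. Section 8.4 restricts blood sampling at ages 8-15 to households where an adult already gives it. Section 11.4 says analyses will adjust for household clustering wherever possible and adds a secondary analysis with one person per household.

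Section 9.9.3 reads zero influenza cases in 750 swabs as "allowing us to rule out virus circulating in more than 0.5% of the community", and gives 1% for RSV with 400 swabs. On selection it says: "A random selection of assay plates will be made at the laboratory on one day of each week".

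**The concern.** Household members share exposure, and the protocol makes within-household association of infection and of immunity secondary objectives (Section 6). When several members of a household give blood, N people carry less information than N independent people. Section 11.3 recognises this for Phase I and makes no allowance for it in the blood margins, and it names no design effect. The intervals later reported under 11.4 should then be wider than those promised.

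The effect is on the stated justification. The drop from 5,500 to 3,600 children is called acceptable on the strength of the 2.7% and 3.3% figures, and the 3.3% is claimed at every seropositivity. A bound stated that way has to hold at 50%, where the interval is widest.

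**Working it through.** **Inputs.**
- N = 10,000 to 15,000, 2,000, 3,600 and 5,500; two groups of 1,800 for the power (11.3).
- Average English region: 125,500 / 9 = 13,944 (target and nine regions, 11.3).
- Participants per household: 2.1 (Lay Summary). This counts everyone aged 2 or over, so it is an assumption when used for adult blood-givers.
- Children per household: 1,465 visited / about 1,100 pilot households = 1.33 (9.4.3). This is also an assumption, since the pilot included ages 5-7 and the 1,100 are invited households.
- Within-household correlation (ICC): not given. Shown from 0.1 to 1, where 1 is the Phase I rule.

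**Step 1: reproduce the plan.** Full Clopper-Pearson 95% width at p = 0.5, N independent people:

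| N | Width | Stated |
|---|---|---|
| 2,000 | 4.43% | below 5% |
| 3,600 | 3.29% | below 3.3% |
| 5,500 | 2.66% | below 2.7% |
| 10,000 | 1.97% | below 2% |
| 13,944 | 1.67% | below 2% |
| 15,000 | 1.61% | below 2% |

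Half-widths (0.99% at 10,000, 1.65% at 3,600) do not match the stated figures. The power for 1,800 against 1,800 is 85.2%. All stated figures agree with a design effect of 1.

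**Step 2: slack.** Replace N by N / DEFF and find the largest DEFF that keeps each bound at p = 0.5:

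| Bound | Largest DEFF |
|---|---|
| 3.3% at 3,600 | 1.004 |
| 2.7% at 5,500 | 1.03 |
| 2% at 10,000 | 1.03 |
| 2% at 13,944 | 1.44 |
| 2% at 15,000 | 1.55 |
| 5% at 2,000 | 1.27 |

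**Step 3: illustrative size.** DEFF = 1 + (m - 1) × ICC, with m people per household. For example, m = 2.1 and ICC 0.2 give DEFF 1.22, effective N = 10,000 / 1.22 = 8,197 and width 2.18%.

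| | ICC 0.1 | 0.2 | 0.5 | 1 |
|---|---|---|---|---|
| 10,000 adults, m = 2.1 | 2.08% | 2.18% | 2.46% | 2.86% |
| 15,000 adults, m = 2.1 | 1.69% | 1.78% | 2.00% | 2.33% |
| 3,600 children, m = 1.33 | 3.35% | 3.40% | 3.56% | 3.80% |

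**Step 4: away from 50%.** With 10,000 adults and full concordance (10,000 / 2.1 = 4,762 effective), the width is 1.73% at 90% seropositive and 0.99% at 97%. The 2% bound holds there.

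**Step 5: power.** If both age groups' variances inflate equally, the 85% falls to 80% at DEFF 1.15 (1,800 / 1.15 = 1,565 per group). Siblings who fall in different age bands would offset part of this loss.

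**Step 6: zero-case limits in 9.9.3.** The upper two-sided 95% limit is 1 - 0.025^(1/n): 0.491% for 750 and 0.918% for 400, matching 0.5% and 1%. If the 750 behave like a simple random 1.08% of the 69,500 weekly swabs (750 / 69,500), the mean number of sampled housemates is about 1.1 × 0.0108 = 0.012. The limit is then 0.496% even at ICC 1.

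**The case against.** The strongest reply is that nothing is miscalculated. Each figure follows from the definition in 11.3, and the household rule was introduced for Phase I infection status as a deliberately conservative choice. Carrying full concordance over to antibodies is not something the protocol asks for. This stands as far as it goes. The point is an undeclared assumption, and the ICC 1 column is an outer limit.

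It is also fair that 10,000 people at 50% is the worst corner. The average region tolerates a design effect of 1.44, and few members of one household fall in the same age band, so the 5% bound is not in real doubt. Section 9.6.1 reports more than 97% positive at the standard threshold, where the 2% bound is safe. This does not rescue the 3.3% figure, which is claimed at any seropositivity.

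The adult and child targets ended in March 2022. The targets that replaced them carry no numerical margin, and 9.4.3 drops the specific child target. That lowers the importance of the point without making the stated figures right.

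A reader might infer two stronger points that the documents do not support:

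- **That the 0.5% influenza limit is wrong.** This would need household members' swabs to share the selected plates. Nothing says they do. Section 9.9.3 expects an approximately random selection of participants, and Step 6 shows the limit then stays below 0.5%. Plate selection makes sharing possible, so the limit rests on an unstated assumption, but it is not shown to be false.
- **That the main regression intervals are too narrow**, because the factors listed in 11.2, besides the time and space terms, "will be sex, age, ethnicity and an age-time interaction". Section 11.4 commits to clustering adjustment wherever possible and to a one-per-household analysis. The factor list alone does not show that the intervals will ignore households.

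**Conclusion.** The concern holds in a limited form and is minor. The blood-sampling margins in 11.3 are correct only at a design effect of 1, which conflicts with household-based sampling, the Phase I unit and the analysis intended in 11.4. Near 50% seropositivity, the 3.3% bound at 3,600 has no usable slack (1.004), and the 2% bound at the lower regional size of 10,000 has very little (1.03). The 2% bound is sturdier at average and large regions and holds at 90% or more seropositive. The 5% bound holds to about 1.27.

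The size of any excess depends on assumptions, because neither the correlation nor the number of blood-givers per household is given. For ICC 0.1 to 0.5 it is about 2.1-2.5% instead of 2% (10,000 adults, 2.1 per household) and 3.35-3.6% instead of 3.3% (3,600 children, 1.33 per household). At ICC 1 the widths are 2.9% and 3.8%. The DEFF formula treats households as equal in size. For 9.9.3, the documents support only the statement that 0.5% and 1% presuppose independent participants.

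**What to change.** In 11.3, restate the 2%, 3.3%, 2.7% and 85% figures with the unit and an assumed design effect, ideally estimated from the blood data already collected, or give them with the household as the unit as in Phase I. Remove the statement that 3.3% holds whatever the true seropositivity.

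In 9.9.3, add a sentence saying that the 0.5% and 1% limits assume independent participants. Swab barcodes link to participants in the study database (9.6.1), so the study can check whether members of one household appear on the same selected plates. If they do, base that week's limit on the number of distinct households.

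The cost is a few sentences, slightly less favourable figures and a simple weekly count for the pilot. No extra samples are needed, and this point calls for no change to the main model.

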11.4. Analysis populations

All enrolled participants will be included in analyses, which will adjust for clustering by household wherever possible. Secondary analysis will also be conducted de-duplicating to one individual per household, for example restricting to adults targeted by ONS in the original approach letter.

11.5. Decision points

Interim analyses will be conducted at least twice a month by statisticians and analysts from the ONS, the University of Oxford and Devolved Administrations (results summarised on https://www.ndm.ox.ac.uk/covid-19/covid-19-infection-survey/results and published by ONS) in order to inform the UK's response to the SARS-CoV-2 pandemic. These interim analyses will follow a standardised format, and will particularly consider prevalence in key subgroups defined by region and age, with additional analyses by sex, ethnicity, occupation, region and symptoms as examples. Results will be available to all organisations involved in conducting the research. Decisions regarding subsequent cross-sectional surveys (and any necessary protocol amendments) will be made by the study management group (see section 13.3 below). Decisions will be reached by consensus wherever possible.

11.6. Stopping rules

There are no formal stopping rules for futility, efficacy or lack of power. The final decision to terminate the study will be made by the Department of Health and Social Care following appropriate consultation and agreement with the Welsh Government, the Department of Health on behalf of the Northern Ireland Government and the Scottish Government.

